2.1. Primary objective

To test the efficacy of early treatment and post exposure prophylaxis to reduce transmission to household family contacts on SARS-CoV-2 PCR assay by day 10.

Measure: Number of household contacts (swab negative on day 1) testing positive for SARS-CoV-2 by PCR on either of three routine nasopharyngeal swabs on day 3, 5 and 10 after enrolment or on clinically driven swab in the first 10 days. Day 1 swab is defined as the swab taken before starting study drug. This could be on the same day as starting study drug.

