2.6 Sample size

For the primary research outcome, a sample size of 120 index cases per arm will provide 80% power. We anticipate that the attack rate for within household transmission will be approximately 85% in the control arm and 75% in the intervention arm. Under these assumptions, in a cluster randomised trial with a binary outcome, assuming an intracluster correlation coefficient of 0.2, an alpha of 0.05 (two sided), and assuming 3 additional household members (in addition to the index case) we have 80% power to detect a reduction in transmission to household contacts. The requisite sample size is then 120 index cases and 360 household contacts per arm. Allowing for 10% loss to follow-up this is increased to 134 index cases (households) per arm, approximately 536 persons per arm. We plan to enroll 268 households and approximately 1072 individuals.

If the household size is 2 additional people, rather than 3, and with all other assumptions the same, we would require 334 households and approximately 1002 individuals. The target sample size for the primary outcome is 1100 individuals enrolled.

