We will summarise the number of participants in each of the 4 categories of the Likert scale in each treatment arm. A mixed effects proportional odds logistic regression will be used to calculate the overall odds ratio, adjusted for the stratification variables and clustered on household. The assumption of proportional odds will be investigated. If it is violated, we will fit a multinomial regression and calculate an odds ratio for each category.

This analysis will also be repeated in the subgroup of participants who tested positive to SARS-CoV-2 infection at baseline.

The following subgroup analyses will be done with the symptom of fatigue as the outcome:

Age: Younger than 65 vs 65 and older

Pre-existing mental health problems: This will be measured by self-reported current comorbidities as mental health disorder (variable mhcat____18).

Previous SARS-CoV-2 infections: Any vs none

These subgroup analyses will be done by including an interaction term between the treatment arm and the subgroup in the mixed effects proportional odds logistic regression model described above. The p-value of the subgroup by arm interaction term will be assessed to determine whether there could be a subgroup effect, with the understanding that the analysis is probably underpowered.

Measure 5.1.2

Each symptom will be assigned a score of 0 if not present, 1 if mild, 2 if moderate and 3 if severe. These scores for each symptom will be added together to get the total neurological long COVID score, ranging from 0 to 66.

Estimand

Population: Household members (older than 5 years) enrolled in the study, regardless of SARS-CoV-2 infection status (all enrolled participants)

Treatment: Initially randomised intervention to unfractionated intranasal heparin 1400u each nostril (as heparin solution 5,000u/ml, 140microL/actuation, TWO actuations each nostril) THREE times daily via a plastic nasal inhalator device or saline control and any subsequent deviations to the per protocol use of the intervention over 10 days

Outcome: Continuous neurological long COVID score (described above) at 6 months, with a 2 month window (i.e. including outcomes measured between 4 and 8 months)

Summary measure: The mean difference between arms will be reported with 95% confidence interval **Potential intercurrent events**:

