Index case in the household not taking study drug. This is defined as compliance <90% Participant (this household member) not taking study drug. This is defined as compliance <90% Either participant (this household member) or index case stop treatment due to adverse event Participant received an anti-viral

Strategy for handling intercurrent event:

All intercurrent events will be handled through the treatment policy strategy, which means that the intercurrent events will be ignored.

The same analysis as described for Measure 4.3 will be done.

This analysis will also be repeated in the subgroup of participants who had SARS-CoV-2 infection.

The following subgroup analyses will be done:

Age: Younger than 65 vs 65 and older

Pre-existing mental health problems: This will be measured by self-reported current comorbidities as mental health disorder (variable mhcat____18).

Previous SARS-CoV-2 infections: Any vs none

These subgroup analyses will be done by including an interaction term between the treatment arm and the subgroup in the model described for Measure 4.3. For example, using the Stata code mixed outcome i.arm##i.subgroup baseline_covariates || household:

The p-value of the subgroup by arm interaction term will be assessed to determine whether there could be a subgroup effect, with the understanding that the analysis is probably underpowered.

Measure 5.1.3

In addition to assessing whether treatment assignment was associated with neurological long COVID we want to investigate whether neurological long COVID outcomes were different for participants who tested positive for SARS-CoV-2 vs those who tested negative.

Estimand

Population: Household members (older than 5 years) enrolled in the study, regardless of SARS-CoV-2 infection status (all enrolled participants)

Exposures compared: Tested positive for SARS-CoV-2 any time during the study (baseline positive or positive during the trial) vs tested negative for SARS-CoV-2 at all time points

Outcome: Ordinal Likert scale measurement of severity of each of the symptoms listed in Measure 5.1.1. at 6 months, with a 2 month window (i.e. including outcomes measured between 4 and 8 months)

Summary measure: The overall odds ratio will be reported with 95% confidence interval

Potential intercurrent events: None

Strategy for handling intercurrent event: Not applicable

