	covariates			
Day 3	Risk difference			
	Risk ratio			
Day 5	Risk difference			
	Risk ratio			
Day 10	Risk difference			
	Risk ratio			
	Repeat for			
	Complete case analysis			
	without covariates			
	Analysis using multiple			
	imputation			
	Hypothetical estimand			

Table 11: Secondary outcome 1: Time to swab negative

	Heparin	Placebo	Hazard ratio (95% CI)
Median (95% CI)			-

Table 12: Secondary outcome 2: Safety of intranasal heparin

	Heparin	Placebo
Number discontinued treatment prior to day 10	N (%) 95% CI	

Table 13: Secondary outcome 3.1: Reduction of symptomatic disease

	Percentag positive N	e testing (%) 95% Cl	Comparison between arms (95% CI)
	Heparin	Placebo	
Treatment policy estimand			
Complete case analysis with covariates			
Risk difference			
Risk ratio			
Complete case analysis without covariates			
Risk difference			
Risk ratio			
Analysis using multiple imputation			
Risk difference			
Risk ratio			

Table 14: Secondary outcome 3.2: Reduction of symptomatic disease

Repeat Table 11

Table 15: Secondary outcomes 4.1 and 4.2: Hospitalisations

		Percentage N (%) 95% (-	Comparison between arms (95% Cl)
		Heparin	Placebo	
Household members				-
	Risk difference	-	-	
	Risk ratio	-	-	
Household members				-
	Risk difference	-	-	
	Risk ratio	-	-	

Table 16: Secondary outcome 4.1: Impact on peak severity of illness (maximum severity score) mean (95%CI)

Heparin	Placebo	Mean difference (95% CI)

Table 17: Secondary outcome 5.1.1. Neurological long COVID at 6 months. Presence of symptoms

	Heparin N (%)			Placebo N (%)				Overall odds ratio	
Symptom	Not present	Mild	Moderate	Severe	Not present	Mild	Moderate	Severe	
Fatigue									
Malaise									
Daytime									
tiredness									
etc									

Table 18: Secondary outcome 5.1.1. Neurological long COVID at 6 months. Presence of symptoms insubgroup of participants who had SARS-CoV-2 infectionRepeat Table 17

Table 19: Secondary outcome 5.1.2. Neurological long COVID at 6 months. Continuous neurological longCOVID score

	Heparin	Placebo	Mean difference (95% CI)
All participants			
Subgroup of			
participants who			
had SARS-CoV-2			
infection			

Table 20: Secondary outcome 5.1.3. Neurological long COVID at 6 months. Presence of symptoms

		SARS-C	oV-2 positive	2	SARS-CoV-2 negative				Overall odds ratio
Symptom	Not present	Mild	Moderate	Severe	Not present	Mild	Moderate	Severe	
Fatigue									
Malaise									
Daytime									
tiredness									
etc									

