Table 21: Secondary outcome 5.1.4. Neurological long COVID at 6 months. Continuous neurological longCOVID score

Heparin	Placebo	Mean difference (95% CI)

Table 22: Secondary outcome 5.1.5. Neurological long COVID at 6 months

Scale	Mear	n (95% CI)	Mean difference between arms (95% CI)	p-value
	Heparin	Placebo		
e.g. WAIS digit span				
DASS etc				
Repeat for subgroup of participants SARS-CoV2 positive				

Table 23: Secondary outcome 5.1.6. Neurological long COVID at 6 months.

Scale	Mean (95% CI)		Mean difference (95%	p-value
			CI)	
	SARS-	SARS-CoV-		
	CoV-2	2 negative		
	positive			
e.g. WAIS digit span				
DASS etc				
Repeat for subgroup of participants SARS-CoV2				
positive				

Table 24: Secondary outcome 5.1.6. Neurological long COVID at 6 months. Subgroup analysesRepeat Table 22 for each subgroup, also include p-value for subgroup

Table 25: Secondary outcome 5.2.1. Neurological long COVID at 6 months. Presence of symptomsRepeat Table 17

Table 26: Secondary outcome 5.2.1. Neurological long COVID at 6 months. Presence of symptoms insubgroup of participants who had SARS-CoV-2 infectionRepeat Table 18

Table 27: Secondary outcome 5.2.2. Neurological long COVID at 6 months. Continuous neurological long COVID score

Repeat Table 19

Table 28: Secondary outcome 5.2.3. Neurological long COVID at 6 months. Presence of symptomsRepeat Table 20

Table 29: Secondary outcome 5.2.4. Neurological long COVID at 6 months. Continuous neurological long COVID score Repeat Table 21

Table 30: Secondary outcome 5.2.5. Neurological long COVID at 6 months.Repeat Table 22

Table 31: Adverse events

	Heparin n (%)	Placebo n (%)
Major bleed		
Nasal itching		
Nose bleed		
HIT		
Local nasal irritation		
Loal or generalized oedema		
Thrombosis		
Sneezing		
Other		
Serious adverse events		
Mean duration of nose bleeds

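### The infected subgroup in long COVID Measures 5.1.2 and 5.1.5 has no time limit, so its arm comparison may select on infections that arise after randomisation

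*SAP*

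**What the plan says.** SAP section 6.5 compares the randomised arms on long COVID outcomes at 6 months in all enrolled participants of eligible age, and repeats three of these comparisons in an infected subgroup. The subgroup is worded in two ways:

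- **Measure 5.1.1** (individual symptoms): "This analysis will also be repeated in the subgroup of participants who tested positive to SARS-CoV-2 infection at baseline".
- **Measures 5.1.2** (total score, 0 to 66) and **5.1.5** (cognition and mood): "This analysis will also be repeated in the subgroup of participants who had SARS-CoV-2 infection". No time point is given.

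The table shells in section 8 do not settle the matter. Table 18 belongs to Measure 5.1.1, but its title gives the subgroup in the wording of 5.1.2, without the baseline limit. Table 19 (for 5.1.2) uses that wording too. Table 22 (for 5.1.5) has "Repeat for subgroup of participants SARS-CoV2 positive", again without a time.

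The only explicit definition of infected participants in section 6.5 is in Measures 5.1.3, 5.1.4 and 5.1.6, which compare infected with uninfected people: "Tested positive for SARS-CoV-2 any time during the study (baseline positive or positive during the trial"). Measure 5.2 repeats Measures 5.1.1 to 5.1.6 at 12 months.

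**The concern.** A subgroup fixed by the day 1 swab is formed before treatment, so the arms within it remain comparable. A subgroup that also admits later infections is formed partly by the trial's primary outcome. Section 2.1 states the aim as to "reduce transmission to household family contacts on SARS-CoV-2 PCR assay by day 10". If heparin works, some people who would have been infected on placebo stay negative on heparin and drop out of the heparin side of the subgroup only. The arms then hold different mixes of people, and a mean difference between them is not a pure treatment effect.

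Two things are at stake. Under the literal reading, a comparison open to selection bias would be reported as a mean difference with a 95% confidence interval, beside the randomised result and without a caveat. Under either reading, the text lets the analyst choose the subgroup after seeing the data, and the three measures may end up with subgroups that do not match.

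**Working it through.** **1. Reproduce the planning figures (section 2.6).** The inputs are attack rates of "approximately 85% in the control arm and 75% in the intervention arm", and "assuming an intracluster correlation coefficient of 0.2, an alpha of 0.05 (two sided"), with 80% power and 3 contacts per household.

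- Per arm without clustering: n = [1.96·√(2·0.80·0.20) + 0.842·√(0.85·0.15 + 0.75·0.25)]² / 0.10² = 250.
- Design effect with 3 contacts: 1 + (3 − 1)·0.2 = 1.4. This gives 250·1.4 = 350 contacts, or 117 households per arm, against the stated 360 and 120 (within 3%).
- Design effect with 2 contacts: 1.2. This gives 300 contacts, or 150 households per arm; 150/0.9 = 167, and 2·167 = 334 households in total, exactly as stated.

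The sample size is not in dispute, so its attack rates are a fair basis for illustration.

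**2. Who enters the subgroup if infection at any time counts.** Let b be the number of day 1 positives in a household of four. The SAP does not give b. One (the index case only) follows the planning model; two is an assumption. Infected members per household are b + (4 − b)·0.85 in control and b + (4 − b)·0.75 on heparin. Counts are for 120 households (480 members) per arm, before age limits and loss to follow-up.

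| b | Control per household | Heparin per household | Control, n | Heparin, n | Infected controls without a heparin counterpart |
|---|---|---|---|---|---|
| 1 | 3.55 | 3.25 | 426 | 390 | 0.30/3.55 = 8.5% |
| 2 | 3.70 | 3.50 | 444 | 420 | 0.20/3.70 = 5.4% |

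The last column assumes that heparin never causes an infection. It counts controls infected after day 1 who would have stayed negative on heparin. Among post-baseline infections alone the share is 0.10/0.85 = 11.8%.

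Later infections would also make up much of the subgroup: 2.55/3.55 = 72% (control) and 2.25/3.25 = 69% (heparin) for b = 1; 1.70/3.70 = 46% and 1.50/3.50 = 43% for b = 2.

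**3. What this does to the score.** Suppose the preventable infections have a mean score d points away from that of the other infected members, and heparin has no effect on the score of those who are infected. The control mean is shifted by s·d, where s is the share in the last column, so heparin minus control is biased by −s·d. The SAP gives no value for d, and its sign is unknown.

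- |d| = 1 point: bias 0.05 (s = 5.4%) to 0.08 (s = 8.5%).
- |d| = 5 points: bias 0.27 to 0.42, on the 0 to 66 scale.

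**4. With the subgroup limited to day 1 positives.** Treatment cannot affect membership, so the expected imbalance from this source is zero.

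**The case against.** The strongest reply is that baseline status may be what the authors meant, and several places support it.

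- Table 18 applies the loose wording to the 5.1.1 subgroup, which the text limits to baseline.
- The clarification of terms at the front of the SAP makes day 1 status the basis for most analyses.
- Section 3.4 lists a day 1 positive population and no ever-infected one.
- Where the SAP wants later infections it says so, as in Measure 1.6 and in 5.1.3, 5.1.4 and 5.1.6. The any-time definition in those last three belongs to a separate, openly non-randomised comparison and is not offered as a general one.

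All of this stands. A reader might infer that the SAP deliberately includes infections after randomisation in this subgroup. The document does not say so; it leaves the timing open.

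The reply does not close the gap, however. The authors wrote the baseline limit in 5.1.1 and left it out of the next measure. Section 3.4 says that sections 5 and 6 specify the population for each objective, and neither 5.1.2 nor 5.1.5 points to the day 1 group for the repeat. Measure 1.6 does plan an arm comparison in a group formed after randomisation, so the literal reading is not far-fetched.

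A second reply is that the effect is small. At any given b, the share of later infections differs between the arms by only about 3 percentage points, and the illustrated score bias is a fraction of a point. This stands as well and limits the weight of the point.

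**Conclusion.** The subgroup in Measures 5.1.2 and 5.1.5 is undefined in time and inconsistent with 5.1.1. If it is read as infection at any time, the arm comparison conditions on the primary outcome and is open to selection bias. With the planned 85% and 75% attack rates, one or two day 1 positives per household of four, and no infections caused by heparin, 5.4% to 8.5% of infected controls would have no heparin counterpart.

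A reader might go further and conclude that the long COVID results as a whole are biased, or biased by a material amount. The documents do not support that. The bias requires the any-time reading, a drug that works, and a score difference d that the SAP does not give; it is probably modest. The main estimands of 5.1.2 and 5.1.5 include participants whatever their infection status and remain randomised comparisons. The issue is confined to a repeat of a secondary analysis, but it should be settled before analysis because the correction is simple.

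**What to change.** In Measures 5.1.2 and 5.1.5, define the subgroup as participants PCR positive on day 1, matching 5.1.1. Carry the same label into Tables 18, 19 and 22 and into the 12-month repeats (Table 26, which repeats Table 18, and Tables 27 and 30, which repeat 19 and 22). Table 22 needs its own edit, because its label differs from the others.

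If an arm comparison in ever-infected participants is still wanted, keep it as a separate analysis, labelled non-randomised and exploratory.

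The change is to SAP wording and table labels only. The price is a smaller subgroup and less precision: in the illustration, 120·1 = 120 to 120·2 = 240 members per arm, instead of 426 to 444 in control and 390 to 420 on heparin.

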3.9. Baseline covariate set

A set of covariates which will be included in models for all primary and secondary outcomes (unless specified otherwise) are: stratification factors (time from positive test to randomisation (binary)) and whether the index case is a child < 5 years(binary), participant age (continuous), inhaled steroid use at baseline (binary), days since symptom onset for index case at randomisation (continuous), whether there are children in the household (binary) and household size (continuous). This is referred to as the baseline covariate set.

Some of these covariates are correlated with each other and may also have sparse data in some of the cells, which may lead to convergence problems with the models. If that is the case, we will exclude some of the baseline covariate set until we can get a model that converges. We will first exclude the sparsest variables, and secondly exclude the variables most correlated with other variables.

We will also repeat each analysis with a model including only the two stratification variables.

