We will summarise the number of participants in each of the 4 categories of the Likert scale in each exposure group. A proportional odds logistic regression will be used to calculate the overall odds ratio, adjusted for the stratification variables and randomised arm and clustered on household. The assumption of proportional odds

will be investigated. If it is violated, we will fit a multinomial regression and calculate an odds ratio for each category.

Measure 5.1.4

In addition to assessing whether treatment assignment was associated with neurological long COVID we want to investigate whether neurological long COVID outcomes were different for participants who tested positive for SARS-CoV-2 vs those who tested negative. The research question is: Does testing positive for SARS-CoV-2 at baseline or during the 10 days of active treatment increase the severity of long COVID symptoms at 6 months?

Estimand

Population: Household members (older than 5 years) enrolled in the study, regardless of SARS-CoV-2 infection status (all enrolled participants)

Exposures compared: Tested positive for SARS-CoV-2 any time during the study (baseline positive or positive during the trial) vs tested negative for SARS-CoV-2 at all time points

Outcome: Continuous neurological long COVID score (described above) at 6 months, with a 2 month window (i.e. including outcomes measured between 4 and 8 months)

Summary measure: The mean difference between SARS-CoV-2 infected and uninfected participants will be reported with 95% confidence interval

Potential intercurrent events: None

Strategy for handling intercurrent event: Not applicable

The two exposures will be compared using mixed effects linear regression with neurological long COVID score as the outcome, adjusting for stratification factors (time from positive test to randomisation, whether the index case is a child < 5 years) randomised treatment arm and the defined baseline covariate set, with household as random effect to take the clustering by household into account.

The mean difference between the exposures will be calculated in Stata as follows using a mixed effects GLM with random intercepts:

mixed outcome i.infection_status i.arm baseline_covariates || household:

Measure 5.1.5

For participants over 16 years of age, cognition and mood were assessed using the harmonised procedures developed by the Neuro-COVID Neuropsychology International Task force. Included measures were:

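### Measure 5.1.3 compares infected with uninfected participants, a non-randomised contrast, without adjusting for age or the other baseline covariates that Measures 5.1.4 and 5.1.6 use for the same exposure

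*SAP*

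**What the plan says.** In SAP Section 6.5, Measures 5.1.3, 5.1.4 and 5.1.6 all compare the same two groups: "Tested positive for SARS-CoV-2 any time during the study (baseline positive or positive during the trial) vs tested negative for SARS-CoV-2 at all time points".

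- **Measure 5.1.3** takes each of the 22 symptoms in turn as a four-level ordinal outcome. The proportional odds model is "adjusted for the stratification variables and randomised arm and clustered on household".
- **Measure 5.1.4** has the same population as 5.1.3 and takes the 0 to 66 sum of those symptoms as its outcome. Its model adjusts for the stratification factors, "randomised treatment arm and the defined baseline covariate set, with household as random effect to take the clustering by household into account". The code is "mixed outcome i.infection_status i.arm baseline_covariates || household".
- **Measure 5.1.6** covers participants older than 16 and the cognition and mood scales. It refers back to 5.1.5, which refers back to Measure 4.3 in Section 6.4, where the full baseline covariate set is used.

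Section 3.9 introduces the default as follows: "A set of covariates which will be included in models for all primary and secondary outcomes (unless specified otherwise) are". The set consists of the two stratification factors plus participant age, inhaled steroid use, days since symptom onset in the index case, presence of children in the household, and household size. Section 3.9 also gives an order for dropping covariates when a model does not converge, and adds: "We will also repeat each analysis with a model including only the two stratification variables".

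Measure 5.2 repeats all of these analyses at 12 months. The SAP gives no reason why 5.1.3 has a shorter list.

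**The concern.** Randomisation does not balance infected and uninfected participants. The infected group contains the index cases, who enter because they are infected, so any systematic difference between index cases and contacts feeds into the comparison. Age is an obvious candidate: participants range from school age to over 65, and age is plausibly related both to being infected and to reporting fatigue, pain, poor sleep or low mood. The SAP itself treats age as relevant to these outcomes. It adjusts for age in 5.1.4 and plans age subgroups for fatigue and for the total score.

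At stake is the interpretation of 22 odds ratios at each of two time points, 22 × 2 = 44 in all. A reader would naturally take them as showing which symptoms follow infection. If part of an odds ratio reflects who became infected, that reading is unsafe.

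**Working it through.** The SAP states no figure on this point, so there is none to reproduce. The check is a comparison of the adjustment sets, followed by two illustrations on assumed inputs.

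**Step 1. Adjustment sets side by side**

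| Covariate | 5.1.3 | 5.1.4 |
|---|---|---|
| Time from positive test to randomisation (stratum) | yes | yes |
| Index case a child under 5 (stratum) | yes | yes |
| Randomised arm | yes | yes |
| Participant age | no | yes |
| Inhaled steroid use | no | yes |
| Days since index symptom onset | no | yes |
| Children in household | no | yes |
| Household size | no | yes |

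Measure 5.1.3 has 3 adjustment variables and 5.1.4 has 3 + 5 = 8.

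**Step 2. Level of the variables in 5.1.3.** Under Section 2.5, both strata describe the index case and the arm is assigned by household. All three take one value per household, so they cannot account for differences between infected and uninfected members of the same household. Allowing for household clustering does not fill the gap. Clustered standard errors change only the precision, and a random intercept would still not adjust for an age difference between two members of one household.

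**Step 3. Does another rule supply the missing covariates?** The Section 3.9 default gives way because 5.1.3 names its own list. The Section 3.9 repeat goes in the reduced direction, to the two strata only. No fuller model for 5.1.3 appears anywhere.

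**Step 4. Hand illustration (all inputs assumed, no true effect of infection).** Suppose fatigue is present in 30% of adults and 10% of children, and that adults make up 75% of the infected and 55% of the uninfected.

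- Infected: 0.75 × 0.30 + 0.25 × 0.10 = 0.25
- Uninfected: 0.55 × 0.30 + 0.45 × 0.10 = 0.21
- Crude odds ratio: (0.25/0.75) / (0.21/0.79) = 1.25

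If the two adult shares are exchanged, the same sum gives (0.21/0.79) / (0.25/0.75) = 0.80. The direction therefore depends on an age pattern that the SAP does not report.

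**Step 5. Ordinal illustration (all inputs assumed).** Proportional odds data were simulated with 20,000 participants, 70% infected, an age standard deviation of 18 years and a true infection odds ratio of 1.00. Each cell gives the estimated infection odds ratio with age omitted and, in brackets, with age included.

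| Mean age gap, infected minus uninfected | Symptom OR 1.1 per 10 years | 1.2 per 10 years | 1.4 per 10 years |
|---|---|---|---|
| 5 years | 1.05 (1.01) | 1.09 (1.01) | 1.18 (1.01) |
| 10 years | 1.08 (0.98) | 1.16 (0.98) | 1.43 (1.05) |
| 15 years | 1.12 (0.95) | 1.28 (0.99) | 1.57 (0.96) |

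Omitting age gives 1.05 to 1.57. Including it gives 0.95 to 1.05, which is 1 within simulation error. As a rough check, the bias should be near (OR per 10 years)^(gap/10): 1.1^0.5 = 1.05 at the low end and 1.4^1.5 = 1.66 at the high end. The simulation has no households or strata and shows only the mechanism.

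**The case against.** The best defence is that the short list is deliberate. Section 3.9 allows exceptions, and the covariates follow the model type: the symptom-by-symptom ordinal models (5.1.1 and 5.1.3) have short lists, and the linear models for the total score (5.1.2 and 5.1.4) have the full set. Sparse data is a plausible reason. Some of the 22 symptoms, such as epilepsy, will be rare, and the multinomial fallback estimates each covariate effect several times over. Measure 5.1.3 can also be read as a descriptive breakdown, since the explicit question whether infection increases severity is posed only in 5.1.4.

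Much of this stands. A reader might infer that the SAP contradicts itself or breaks its own covariate rule. It does not, because 5.1.3 uses the exception that Section 3.9 provides. A reader might also infer that any disagreement between 5.1.3 and 5.1.4 would show confounding. That does not follow either: odds ratios for single symptoms and a mean difference on a sum need not agree even with identical covariates.

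The defence does not remove the confounding point. In 5.1.1 a short list is defensible because the arms are randomised; in 5.1.3 the exposure is observational. Sparse symptoms are already covered by the Section 3.9 convergence rule, so age need not be left out of all 22 models in advance. The descriptive reading is only partial mitigation, because 5.1.3 still reports an adjusted odds ratio and 5.1.4 opens with the same general aim.

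**Conclusion.** The point holds as a weak analysis choice. Measure 5.1.3 is the only one of the three infection-status comparisons with no participant-level adjustment, and its odds ratios may be confounded by age and household make-up.

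It would be tempting to say that the odds ratios are confounded, or inflated by about a quarter. The SAP does not support that. It gives neither age by infection status nor symptom frequency by age, so neither size nor direction can be known. The figures of 1.25 and of 1.05 to 1.57 are purely hypothetical. The first is also a crude odds ratio, whereas 5.1.3 does adjust for strata and arm.

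The consequence is limited to a secondary, non-randomised comparison at 6 and 12 months. The primary outcome and every comparison of randomised arms are untouched. The change is a cheap improvement and not a necessary correction.

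**What to change.** In Measure 5.1.3, and so in its 12-month repeat under 5.2:

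1. Fit each ordinal model with infection status, randomised arm and the Section 3.9 baseline covariate set, keeping the household clustering.
2. Where the model for a rare symptom does not converge, drop covariates by the existing Section 3.9 rule and report beside that odds ratio which were dropped.
3. Keep the present strata-plus-arm model as a named secondary run. It must be written into 5.1.3, because the Section 3.9 repeat contains only the two strata and so is not the same model.

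The cost is a wording change. The covariates are already needed for 5.1.4 in the same participants. There are two drawbacks: adjustment sets may differ across rare symptoms, and residual confounding will remain because the baseline set omits other recorded characteristics such as sex, vaccination and previous infection. If the short list is kept, a sentence giving the reason would resolve the unexplained difference but not the confounding.
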